9.10.2 Criteria for Temporary Halt of Vaccinations in All Volunteers

All vaccinations as part of this study will be suspended (i.e. no further vaccinations will be given to any participant) if any of the following criteria arise:

1. One volunteer experiences an SAE that is possibly, probably or definitely related to the investigational product(s).
2. Two unforeseen severe AEs occur which are deemed clinically significant by the LSM. (All severe AEs will be reviewed in the study.)
3. One volunteer experiences injection site ulceration, sterile abscess or necrosis possibly, probably or definitely associated with vaccine administration.
4. One volunteer experiences a severe allergic reaction, such as laryngospasm, bronchospasm or anaphylaxis, possibly, probably or definitely associated with vaccine administration.
5. One volunteer experiences a life-threatening event or death regardless of the causality.

Vaccinations may be recommenced only if it is deemed safe to recommence by the LSM, the MHRA, the ethics committee and the study investigators following the procedures below. Procedures to follow after discontinuing vaccinations:

If vaccinations are suspended MHRA and REC will be notified within 15 days with a substantial amendment, using the notification of amendment form, clearly explaining the reason for the halt of vaccinations. In addition, the Investigators will request a review by the LSM, to be held within two business days of the Investigators learning of the event. No additional vaccinations will be given until the opinion of the LSM has been sought. However, all volunteers will remain in the study for

immunological and safety follow up. To restart vaccinations, a further request as a substantial amendment, providing evidence that it is safe to restart the trial should be made to MHRA and REC.

In addition to these pre-defined criteria, the study can be put on hold upon advice of the Local Safety Monitor, CI, Study Sponsor, Regulatory Authority, or Ethical Committee(s), for any single event or combination of multiple events which, in their professional opinion, jeopardises the safety of the participants or the reliability of the data.

10. STATISTICS

The primary objective of this study is to assess the safety of ChAdOx1.tHIVconsV1 and MVA.tHIVconsV3&4 vaccines in healthy volunteers. In total, thirteen subjects will be recruited into the study. Our experience from previous clinical trials with similar vaccines suggests that this sample size is a feasible number to recruit, screen, enrol and follow-up in practical terms, whilst also allowing the evaluation of the safety and immunogenicity of the proposed vaccine regimens.

In view of the unlikely occurrence of a SUSAR with these vaccines based on our experience of working with similar vaccines, it is not the remit of this study to recruit sufficient numbers of volunteers to be statistically confident about the efficacy results. Therefore the safety data will be primarily descriptive. The incidence of mild, moderate or severe AEs will be used as a measure of safety of the investigational products. From previous experience with similar vaccines, the proposed number of participants should be sufficient to determine the risk of serious AEs or severe local or systemic reactions in healthy volunteers.

Summary statistics will be calculated; point and interval estimates of AEs and immune responses will be reported.

Based on previous experience with similar trials, it is expected that the amount of missing, unused or spurious data will be insignificant. Unused and spurious data will be listed separately and excluded from the statistical analysis. Missing data will be excluded from the statistical analysis.

All volunteers who receive at least one vaccination will be included in the analysis.

Statistical analysis will be performed with the support of a qualified statistician based at the Primary Care trials unit, Oxford. Analysis will be conducted according to local SOPs and an agreed Statistical Analysis Plan.

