5.1 Rationale for selected doses

The total doses employed as well as the heterologous-prime-boost chimp adenovirus-MVA regimen have been tested and optimised for these types of vaccine vectors in many human volunteers for HIV-1 and other disease candidate vaccines.

A first-in-human dose escalation study using the ChAdOx1 vector encoding an influenza antigen (FLU004), safely administered ChAdOx1 NP+M1 at doses ranging from 5×10^8 to 5×10^{10} vp. In two clinical studies conducted in Oxford (CHIK001 and MERS001), ChAdOx1 vector was administered at the dose 5×10^{10} vp to 18 healthy volunteers, with no safety concerns. ChAdOx1 vectored vaccines have thus far been demonstrated to be very well tolerated. The vast majority of AEs have been mild-moderate and there have been no SARs reported to date.

ChAdOx1.tHIVcons1 (C1) has not been tested on humans before, and the first three participants will receive a low dose of the vaccine (group 1). After safety review, the next 10 volunteers (group 2) will receive a higher dose of C1, followed by MVA.tHIVcons3 & 4 (M3M4). The 4-week interval was shown to be equivalent to the 8-week interval in the HIV-CORE 003 trial and studies with Ebola vaccines ([name], UOXF; personal communication).

The optimal dose of rMVAs were shown consistently to be $1-2 \times 10^8$ pfu. Higher doses of rMVAs ($2.5-5 \times 10^8$ pfu) were associated with marked reactogenicity, with severe 'flu-like' systemic AEs recorded in a previous study in Oxford. Lower doses of rMVAs enable an acceptable reactogenicity profile without significantly compromising vaccine immunogenicity.

Clinical studies have shown IM administration to be associated with fewer and short-lived local AEs and no reduction in immunogenicity⁽⁴⁰⁾.

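### Section 10 claims the sample is enough to determine the risk of serious AEs and severe reactions; no events in the 10 full-regimen volunteers would still be compatible with a risk of up to 31% (exact two-sided 95% limit)

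*Combined protocol and SAP*

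**What the plan says.** The sample-size rationale is in Section 10 (Statistics). Thirteen volunteers are justified by feasibility and by experience with similar vaccines. No event rate, confidence level, precision target or detection probability is given.

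The second paragraph of that section makes these statements, in this order:

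- It opens with "In view of the unlikely occurrence of a SUSAR with these vaccines" and says that recruiting enough volunteers to be "statistically confident about the efficacy results" is outside the study's remit.
- It continues: "Therefore the safety data will be primarily descriptive".
- It ends by saying that, from earlier experience, "the proposed number of participants should be sufficient to determine the risk of serious AEs or severe local or systemic reactions in healthy volunteers".

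The next paragraph says that "point and interval estimates of AEs and immune responses will be reported", without naming a confidence level or interval method. An agreed Statistical Analysis Plan is mentioned, but its text is not included.

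Table 1 in Section 5.2 splits the 13 volunteers into Group 1 (3, low-dose ChAdOx1.tHIVconsv1 only) and Group 2 (10, high-dose ChAdOx1.tHIVconsv1 followed by the two MVA vaccines). The Synopsis lists the proportion with vaccine-related SAEs as a primary endpoint. On ChAdOx1-vectored vaccines generally, Section 5.1 reports: "The vast majority of AEs have been mild-moderate and there have been no SARs reported to date".

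**The concern.** To determine a risk is to estimate it closely enough to say whether it is low or high. Ten volunteers cannot do that for an event that the protocol itself expects to be rare. Section 10 calls a SUSAR unlikely, and under Section 9.2 every serious adverse reaction in this trial would be reported as a SUSAR. A zero count for the vaccine-related SAE endpoint is therefore a plausible outcome by the protocol's own account.

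What is at stake is how that zero would be read. Under the Section 10 sentence it can be taken as a risk that has been measured and found low. Section 3.3.5 says the data will inform the design of similar studies in other populations, so that reading could be carried forward.

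The protection of participants does not depend on the sentence. It comes from the staggered enrolment in Section 5.2.1 and the halting criteria in Section 9.10.2, under which one related SAE suspends all vaccinations.

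**Working it through.** The plan gives no calculation for 13, so there is no figure to reproduce beyond 3 + 10 = 13, which agrees with Table 1. The check asks what these group sizes can show.

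**Inputs.** n = 10 (Group 2), n = 3 (Group 1) and n = 13 (all vaccinated volunteers, the analysis population in Section 10). Section 10 gives no confidence level or method, so exact (Clopper-Pearson) two-sided 95% intervals are assumed, and other methods are shown for comparison.

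**1. Upper limit for the true risk when no event is seen.** The formula is 1 − 0.025^(1/n).

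| Group | n | Calculation | Upper limit |
|---|---|---|---|
| Group 1 | 3 | 1 − 0.292 | 70.8% |
| Group 2 | 10 | 1 − 0.692 | 30.8% |
| Pooled across doses and regimens | 13 | 1 − 0.753 | 24.7% |

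**2. Sensitivity to the method, for 0 of 10.**

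- Jeffreys, two-sided 95%: 21.7%
- Exact, one-sided 95%: 1 − 0.05^(1/10) = 25.9%
- Wilson, two-sided 95%: 1.96² / (10 + 1.96²) = 27.8%
- Exact, two-sided 95%: 30.8%

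Even the smallest of these is above 20%.

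**3. One event seen.** For 1 of 10 the exact 95% interval is 0.3% to 44.5%.

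**4. Chance of seeing at least one event in 10.** The formula is 1 − (1 − p)^10, where p is the true risk.

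| True risk | Chance of no event | Chance of at least one |
|---|---|---|
| 1% | 0.99^10 = 90.4% | 9.6% |
| 5% | 0.95^10 = 59.9% | 40.1% |
| 10% | 0.90^10 = 34.9% | 65.1% |
| 20% | 0.80^10 = 10.7% | 89.3% |

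**5. True risk that 10 volunteers would probably reveal.** For an 80% chance of at least one event, p = 1 − 0.2^(1/10) = 14.9%. For a 90% chance, p = 1 − 0.1^(1/10) = 20.6%.

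**6. Where severe reactions fall on this scale.** The documents give no rate at the trial doses. Section 5.1 describes most ChAdOx1 AEs as mild to moderate. It links severe influenza-like "systemic AEs recorded in a previous study in Oxford" to rMVA doses of 2.5–5 × 10^8 pfu, whereas the two MVA components here total 1.0 + 0.9 = 1.9 × 10^8 pfu. Nothing in the text therefore shows that severe reactions are expected at 15% or more, where 10 volunteers would probably reveal them.

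**The case against.** The strongest defence is that the sentence does little work and is already softened. The safety analysis is described as descriptive, interval estimates are promised, and the sentence opens by appealing to earlier experience. A reported interval for 0 of 10 would itself show the reader how little is known. No planned analysis or decision uses the claim, and small numbers are normal in phase 1.

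Much of this is fair. It means that the sample size is not in question and that the remedy is a change of wording. It does not make the sentence true:

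- The descriptive statement comes earlier in the same paragraph, and the sufficiency claim follows it without qualification.
- Section 10 plans no borrowing of earlier data, so this trial's intervals rest on its own 10 and 3 volunteers. Experience with similar vaccines can support an expectation of low risk, but it cannot make 10 volunteers enough to measure that risk.
- The unseen Statistical Analysis Plan may supply the interval method, but that would not correct the protocol's claim.

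Three further points affect precision but not the conclusion. The 31% depends on the assumed exact two-sided 95% limit, and other usual methods give 22% to 28%. For reactions to any dose of ChAdOx1.tHIVconsv1 the denominator could be 13, giving 24.7%. And because one related SAE suspends vaccination, fewer than 10 might be dosed, which would widen the intervals further.

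On the efficacy wording, the opening reference to SUSARs and the sentence that follows suggest that safety was probably meant. The paragraph would then disclaim statistical confidence about safety and go on to claim sufficiency for it. If efficacy is literal, it refers to something for which no endpoint is listed, and nothing disclaims the safety claim. Either way the sponsor needs to clarify it.

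**Conclusion.** The concern holds. Section 10 attributes to the sample size a capability it does not have. With no events in Group 2, a true risk of up to 30.8% remains compatible with the data (21.7% to 30.8% across the usual interval methods), and a true risk of 10% is missed about one time in three.

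The challenge is strongest for serious AEs, where a zero count is plausible and would be uninformative about rare risk. It is weaker for severe local or systemic reactions: one with a true risk of about 15% or more would probably be seen at least once. Seeing it would still not fix its rate, as the interval for 1 of 10 shows.

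The results assume 95% confidence, independent volunteers and all 10 Group 2 volunteers dosed and followed. The finding concerns the stated justification only and should be corrected.

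**What to change.** Replace the sufficiency sentence in Section 10 with a statement of attainable precision, for example:

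> With 10 volunteers on the full regimen there is an 80% (90%) chance of observing at least one event whose true risk is about 15% (21%). If none is observed, the exact 95% confidence interval is 0–31% (0–71% for Group 1, n = 3). The trial can describe common reactions but cannot determine the risk of serious AEs or of uncommon severe reactions.

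State, here or in the agreed Statistical Analysis Plan, that the interval estimates already planned for AEs will be exact 95% intervals reported by group. Ask the sponsor to confirm whether the words on efficacy results should refer to safety results, and correct them if so.

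The cost is one sentence replaced, one word confirmed and an interval method named. The only drawback is a less favourable description of what the trial can show.

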11. DATA MANAGEMENT

11.1 Data Handling

The CI will be responsible for all data that accrues from the study. The data will be captured directly into the volunteers' electronic CRFs or transferred from a paper source in to the eCRF created on the study specific database. Electronic data will be stored on secure servers. Data will be entered directly into the study database via a stand-alone password protected app. The study specific database meets 21 CFR part 11 FDA standards. This includes safety data, including laboratory safety data and outcome data.

All AE data (both solicited and unsolicited) reported by the volunteer will be entered onto a volunteer's electronic diary card (eDiary) for a maximum of 28 days following administration of the IMP. The eDiary provides a full audit trail of edits and will be reviewed at each review time-points indicated in the schedule of events. Any AE continuing beyond the period of the diary will be copied into the eCRF and followed to resolution, if there is a causal relationship to the IMP, or to the end of the study if there is no causal relationship.

11.2 Record Keeping

The Investigators will maintain appropriate medical and research records for this trial, in compliance with GCP and regulatory and institutional requirements for the protection of confidentiality of volunteers. The CI, co-Investigators and clinical research nurses will have access to records. The Investigators will permit authorised representatives of the Sponsor(s), as well as ethical and regulatory agencies to examine (and when required by applicable law, to copy) clinical records for the purposes of quality assurance reviews, audits and evaluation of the study safety and progress.

With the volunteers' consent, we will keep their contact details after participation in the study is complete, so we may inform them of opportunities to participate in future vaccine related research. This will be entirely optional and participation in this study will not be affected by their decision to allow or not allow storage of their contact details beyond participation in this trial. Details will be stored electronically on a secure server and only authorised individuals at the CCVTM will have access to it. We will not, under any circumstances, share their contact details with any third party institutions without their permission. Volunteers will be informed that being contacted does not oblige them to

agree to take part in future research and they can ask us to have their contact details removed from our database at any time.

11.3 Source Data and Case Report Forms (CRFs)

All protocol-required information will be collected in CRFs designed by the Investigator. All source documents will be filed in the CRF. Source documents are original documents, data, and records from which the volunteer's CRF data are obtained. For this study, these will include, but are not limited to, volunteer consent form, blood results, GP response letters, laboratory records, diaries, and correspondence. In the majority of cases, CRF entries will be considered source data as the CRF is the site of the original recording (i.e. there is no other written or electronic record of data). In this study this will include, but is not limited to medical history, medication records, vital signs, physical examination records, urine assessments, blood results, AE data and details of vaccinations. All source data and volunteer CRFs will be stored securely.

11.4 Data Protection

The study will comply with the UK General Data Protection Regulation (GDPR) and Data Protection Act 2018, which require data to be de-identified as soon as it is practical to do so. The processing of the personal data of participants will be minimised by making use of a unique participant study number only on all study documents and any electronic database(s). All documents will be stored securely and only accessible by study staff and authorised personnel. The study staff will safeguard the privacy of participants' personal data. No information concerning the study or the data will be released to any unauthorised third party, without prior written approval of the Sponsor.

11.5 Data Quality

Data collection tools will undergo appropriate validation to ensure that data are collected accurately and completely. Datasets provided for analysis will be subject to quality control processes to ensure analysed data is a true reflection of the source data.

Trial data will be managed in compliance with local data management SOPs (including the overarching SOP OVC1913 Data and Database Management for DF/Net Studies). If additional, study-specific information is required, an approved Data Management Plan will be implemented.

12. QUALITY CONTROL AND QUALITY ASSURANCE PROCEDURES

12.1 Investigator procedures

Approved site-specific standard operating procedures (SOPs) will be used at all clinical and laboratory sites.

12.2 Monitoring

Regular monitoring will be performed according to GCP by the sponsor (CTRG). Following written SOPs, the monitor will verify that the clinical trial is conducted and data are generated, documented and reported in compliance with the protocol, GCP and the applicable regulatory requirements. The site will provide direct access to all trial related source data/documents and reports for the purpose of monitoring and auditing by the Sponsor and inspection by local and regulatory authorities.

12.3 Protocol deviation

Any deviations from the protocol will be documented in a protocol deviation form and filed in the trial master file. Each deviation will be assessed as to its impact on volunteer safety and study conduct. Protocol deviations will be listed in the end of study report.

12.4 Audit & inspection

The QA manager conducts systems based internal audits to check that trials are being conducted according to local procedures and in compliance with GCP and applicable regulations.

The Sponsor, trial sites, and ethical committee(s) may carry out audits to ensure compliance with the protocol, GCP and appropriate regulations.

GCP inspections may also be undertaken by the MHRA to ensure compliance with protocol and the Medicines for Human Use (Clinical Trials) Regulations 2019, as amended. The Sponsor will assist in any inspections and will support the response to the MHRA as part of the inspection procedure.

13. SERIOUS BREACHES

The Medicines for Human Use (Clinical Trials) Regulations contain a requirement for the notification of "serious breaches" to the MHRA within 7 days of the Sponsor becoming aware of the breach.

A serious breach is defined as "A breach of GCP or the trial protocol which is likely to effect to a significant degree

- (a) the safety or physical or mental integrity of the subjects of the trial; or
- (b) the scientific value of the trial".

In the event that a potential serious breach is suspected the Sponsor will be informed as soon as possible, to allow preliminary assessment of the breach and reporting to the MHRA within the required timelines.

14. ETHICS AND REGULATORY CONSIDERATIONS

14.1 Declaration of Helsinki

The Investigators will ensure that this study is conducted according to the principles of the current revision of the Declaration of Helsinki.

14.2 Guidelines for Good Clinical Practice

The Investigator will ensure that this trial is conducted in accordance with relevant regulations and with Good Clinical Practice.

14.3 Ethical and Regulatory Approvals

Following sponsor approval, the protocol, informed consent form, participant information sheet and any proposed advertising material will be submitted to an appropriate Research Ethics Committee (REC), HRA (where required), regulatory authorities (MHRA in the UK), and host institution(s) for written approval.

No substantial amendments to this protocol will be made without consultation with, and agreement of, the Sponsor. Any substantial amendments to the trial that appear necessary during the course of the trial must be discussed by the Investigator and Sponsor concurrently. If agreement is reached concerning the need for an amendment, it will be produced in writing by the CI (or delegate) and will be made a formal part of the protocol following ethical and regulatory approval.

The Investigator is responsible for ensuring that changes to an approved trial, during the period for which regulatory and ethical committee(s) approval has already been given, are not initiated without regulatory and ethical committee(s)' review and approval except to eliminate apparent immediate hazards to the subject (i.e. as an Urgent Safety Measure).

14.4 Reporting

The CI shall submit once a year throughout the clinical trial, or on request, an Annual Progress Report to the REC, HRA (where required), host organisation, funder (where required) and Sponsor. In addition, an End of Trial notification and final report will be submitted to the MHRA, the REC, host organisation and Sponsor.

14.5 Transparency in Research

Prior to the recruitment of the first participant, the trial will have been registered on a publicly accessible database.

Results will be uploaded to the European Clinical Trial (EudraCT) Database within 12 months of the end of trial declaration by the CI or their delegate.

Where the trial has been registered on multiple public platforms, the trial information will be kept up to date during the trial, and the CI or their delegate will upload results to all those public registries within 12 months of the end of the trial declaration.

14.6 Volunteer Confidentiality

All data will be anonymised: volunteer data will be identified by a unique study number in the CRF and database. A separate confidential file containing identifiable information will be stored in a secured location in accordance with the relevant data legislation. Only the Sponsor representative, Investigators, the clinical monitor, the REC and the MHRA will have access to the records. Photographs taken of vaccination sites (if required, with the volunteer's written, informed consent) will not include the volunteer's face and will be identified by the date, trial code and subject's unique identifier. Once developed, photographs will be stored as confidential records, as above. This material may be shown to other professional staff, used for educational purposes, or included in a scientific publication.

